### **8.1.1 Baseline Characteristics**

All baseline summary statistics and analyses will be based on characteristics obtained prior to the initiation of study drug (or randomization for non-treated subjects). Unless otherwise stated, baseline for a given variable will be defined as the last value for that variable obtained prior to the first dose of study drug.

#### **8.1.1.1 Demographics**

Continuous demographic data (e.g., age, height, and weight) will be summarized with means, standard deviations, medians, and minimum and maximum values. Frequencies and percentages will be computed for categorical data (e.g., sex, race, and performance status).

Smoking history can be defined as current smoker (subject who has smoked within the last 12 months and has more than 100 smoking events [for example, cigarettes] in their lifetime), never smoked (subject with a lifetime smoking history of  $\leq 100$  smoking events [for example, cigarettes] in lifetime) and past smoker (subject who has not smoked in past 12 months and has more than 100 smoking events [for example, cigarettes] in their lifetime).

#### **8.1.1.2 Medical History**

Frequencies and percentages will be computed for each medical history parameter.

### **8.1.2 Efficacy Endpoints**

#### **8.1.2.1 Primary Efficacy Endpoint**

The primary efficacy endpoint is progression-free survival (PFS).

Progression-free survival will be defined as the number of days from the date of randomization to the date of earliest disease progression (radiographic progression per RECIST version 1.1) or death. All events of disease progression will be included, regardless of whether the event occurred while the subject was still taking study drug or had previously discontinued study drug. If the subject does not have an event of disease progression nor has the subject died, the subject's data will be censored at the date of the subject's last available radiographic disease progression assessment.

### **8.1.2.2 Secondary Efficacy Endpoints**

Secondary efficacy endpoints include objective response rate and overall survival.

#### **Objective Response Rate**

The proportion of subjects with objective response (CR or PR) as assessed by the investigator using RECIST version 1.1 will be evaluated for randomized subjects.

#### **Overall Survival**

Overall survival will be defined as the number of days from the date of randomization to the date of death. For subjects who did not die, their data will be censored at the date of last study visit or the last known date to be alive, whichever is later.

### **8.1.2.3 Tertiary Efficacy Endpoints**

In addition to the primary and secondary efficacy analyses, tertiary efficacy analyses of duration of overall response and performance status will be performed.

#### **Duration of Overall Response**

Duration of overall response will be defined as the number of days from the date of first response (CR or PR) to the earliest documentation of radiographic progressive disease. If a subject is still responding, then the subject's data will be censored at the date of the subject's last available disease assessment (radiographic or clinical). For subjects who never experience response, the subject's data will not be included in the analysis.

## **Performance Status**

ECOG performance status will be determined by the investigator at assessment throughout therapy and at the final visit.

### **8.1.3 Primary Analysis of Efficacy**

PFS will be analyzed by Kaplan-Meier methodology and compared between Arm A (veliparib in combination with carboplatin/etoposide followed by veliparib monotherapy) and Arm C (placebo in combination with carboplatin/etoposide followed by placebo monotherapy), using a log-rank test stratified by LDH level. A two-sided, stratified log-rank test *P* value will be provided. Median PFS time will be calculated and 95% confidence interval for median PFS time will be presented. A hazard ratio estimate (Arm A versus Arm C) and the corresponding 95% confidence interval will be obtained from a Cox proportional hazards model.

### **8.1.4 Secondary Analysis of Efficacy**

#### **8.1.4.1 Progression-Free Survival (Arm B Versus Arm C)**

PFS will be analyzed by Kaplan-Meier methodology and compared between Arm B (veliparib in combination with carboplatin/etoposide followed by placebo monotherapy) and Arm C, using a log-rank test stratified by LDH level. A two-sided, stratified log-rank test *P* value will be provided. Median PFS time will be calculated and 95% confidence interval for median PFS time will be presented. A hazard ratio estimate (Arm B versus Arm C) and the corresponding 95% confidence interval will be obtained from a Cox proportional hazards model.

#### **8.1.4.2 Objective Response Rate**

The objective response rate at the time of completion of combination therapy will be estimated and compared between Arm A + B combined and Arm C, using a Cochran-Mantel-Haenszel test stratified by LDH level. A two-sided, stratified CMH test

*P* value will be provided. In addition, a 95% confidence interval will be constructed for the estimated proportions.

#### **8.1.4.3 Overall Survival**

OS will be analyzed by Kaplan-Meier methodology and compared between Arm A and Arm C as well as between Arm B and Arm C, using a log-rank test stratified by LDH level. A two-sided, stratified log-rank test *P* value will be provided. Median OS time will be calculated and 95% confidence interval for median OS time will be presented. Hazard ratio estimates (Arm A versus Arm C, Arm B versus Arm C) and the corresponding 95% confidence intervals will be obtained from a Cox proportional hazards model.

#### **8.1.5 Tertiary Analysis of Efficacy**

##### **8.1.5.1 Duration of Overall Response**

The distribution of duration of overall response (DOR) will be estimated for each treatment arm using Kaplan-Meier methodology. Median DOR will be estimated and a 95% confidence interval will be presented for each treatment arm.

##### **8.1.5.2 Progression-Free Survival (Arm A Versus Arm B)**

PFS will be analyzed by Kaplan-Meier methodology and compared between Arm A and Arm B, using a log-rank test stratified by LDH level. A two-sided, stratified log-rank test *P* value will be provided. Median PFS time will be calculated and 95% confidence interval for median PFS time will be presented. A hazard ratio estimate (Arm A versus Arm B) and the corresponding 95% confidence interval will be obtained from a Cox proportional hazards model.

##### **8.1.5.3 Overall Survival (Arm A Versus Arm B)**

OS will be analyzed by Kaplan Meier methodology and compared between Arm A and Arm B, using a log-rank test stratified by LDH level. A two-sided, stratified log-rank test *P* value will be provided. Median OS time will be calculated and 95% confidence interval for median OS time will be presented. A hazard ratio estimate (Arm A versus Arm B)

and the corresponding 95% confidence interval will be obtained from a Cox proportional hazards model.

#### **8.1.5.4 ECOG Performance Status**

Changes and/or percent changes from baseline in ECOG performance status will be summarized using descriptive statistics for each scheduled post-baseline visit and for the final visit. Post-baseline measurements more than 30 days after the last dose of study drug will not be included. Subjects that do not have a baseline measurement or do not have any post-baseline measurements will not be included. Changes and/or percent changes from baseline to each visit will be compared between Arm A and Arm C as well as between Arm B and Arm C using an analysis of covariance with treatment arm as the factor and baseline value as a covariate.

#### **8.1.6 Pharmacokinetics**

##### **8.1.6.1 Tabulations and Summary Statistics**

Plasma concentrations and pharmacokinetic parameter values of veliparib, carboplatin, and etoposide will be tabulated for each subject by dose level, and summary statistics will be computed for each sampling time and each parameter by dose level.

##### **8.1.6.2 Model and Tests**

##### **Dose Proportionality of Veliparib on Phase 1 Cycle 1 Day 1**

To address the issue of dose proportionality for designated veliparib doses, a linear mixed effects model analysis will be performed for dose-normalized  $C_{\max}$  and  $AUC_{0-8}$  and other pharmacokinetic parameters provided that they can be adequately determined from the data. The natural logarithmic transformation will be employed for  $C_{\max}$  and the AUC's unless the data clearly indicate that other transformation or the untransformed variable provides more nearly symmetric probability distributions and/or more nearly homogenous variances across dose levels. The model will include dose level, this may be done by classifying subjects by dose level or, if appropriate, using dose level as a continuous

variable. Some variables such as age, body weight, gender, and perhaps others that might explain some of the variability in the population will be included in the model initially as covariates. A necessary condition for a variable to be included in the final model is that the regression coefficient be significant at level 0.10. The dependence among explanatory variable candidates will also be considered when selecting the final model.

Within the framework of the final model, the null hypothesis of no difference between the means of the highest and lowest veliparib doses will be tested. Assuming that at least four veliparib dose levels are indeed studied, a test will also be performed on a contrast in the dose level, with the contrast chosen to be sensitive to an approximately linear function of dose or the logarithm of dose.

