## **5.0 Investigational Plan**

### **5.1 Overall Study Design and Plan: Description**

This is a Phase 1, open-label, dose escalation/Phase 2 randomized double-blind study of veliparib in combination with carboplatin and etoposide and maintenance veliparib monotherapy. Subjects in Phase 1 will be group sequentially assigned to the ascending dose levels of veliparib in combination with standard carboplatin/etoposide regimen based on the observed toxicities. Subjects in Phase 2 will be randomized in a 1:1:1 ratio to carboplatin, etoposide, placebo followed by placebo maintenance, or carboplatin, etoposide, veliparib followed by either veliparib or placebo maintenance. Approximately 215 adult male or female subjects diagnosed with extensive stage disease SCLC or other advanced/metastatic solid tumors will be selected to participate in the study according to the inclusion/exclusion criteria.

The study was designed to enroll approximately 35 subjects in Phase 1 and approximately 180 subjects in Phase 2 to meet scientific and regulatory objectives without enrolling an undue number of subjects in alignment with ethical considerations. Possible dose levels to be evaluated are as shown in [Table 4](#).

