**Table 4. Phase 1 Dose Escalation**

Dose Level	Number of Subjects	Doses		
		Veliparib mg	Carboplatin AUC, mg/mL*min	Etoposide mg/m 
I	3 – 9	80	5	100
II	3 – 6	120	5	100
III	3 – 6	160	5	100
IV	3 – 6	200	5	100
V	3 – 6	240	5	100
VI	3 – 6	300	5	100
VII	3 – 6	340	5	100
VIII	3 – 6	400	5	100

A "3 + 3" escalation rule will be used for the dose-escalation portion of this study, with a condition applied for the Dose Level 1, which will allow 3 additional subjects to be entered in Dose Level 1 if 2 of 6 initial subjects experience DLTs. Enrollment of the 3 additional subjects at all dose levels will depend on a review of the specific DLTs observed and discussion with the Investigators.

A minimum of 3 evaluable subjects will be enrolled at each dose level. Additional eligible subjects may be enrolled at the current dose level at the discretion of the Investigators and the AbbVie TA MD. The dose escalation decisions will be made following the completion of the DLT observation period for the evaluable subjects in the intended cohort size. If a cohort is over-enrolled, reported toxicities in additional subjects will be taken into consideration.

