the overall safety profile of the study drug. The RPTD cannot exceed the lower of the MTD or MAD. At the RPTD and schedule additional subjects will be added as needed so that a total of at least 9 subjects will be treated at the RPTD.

DLT Definition: DLT is defined as any of the following drug-related toxicities occurring during the DLT observation period (Cycle 1 Day -2 to Cycle 2 Day 1) in any of the dose-escalation cohorts, with grading according to the National Cancer Institute (NCI) Common Toxicity Criteria for Adverse Events (CTCAE), version 4.0^20:

1. Cycle 1 events associated with treatment delay > 14 days in initiating Cycle 2 chemotherapy:
  - a. Grade 4 thrombocytopenia (platelets <  $25.0 \times 10^9/L$ )
  - b. Grade 4 neutropenia (absolute neutrophil count (ANC) <  $0.5 \times 10^9/L$ )
  - c. Grade 3 febrile neutropenia with fever lasting for > 7 days
  - d. Grade 4 febrile neutropenia of any duration

NOTE: Delay of more than 14 days in initiating Cycle 2 due to factors not directly related to treatment emergent toxicity will not be considered a DLT.

2. Grade  $\geq 3$  non-hematologic toxicity that represents at least 2 grade increase from baseline and is attributed to veliparib treatment:
  - a. Exclusion: nausea and vomiting lasting  $\leq 48$  hours or inadequately treated
  - b. Exclusion: electrolyte abnormalities resolving within  $\leq 24$  hours
  - c. Exclusion: hypersensitivity reactions
  - d. Exclusion: alopecia
3. Grade 2 non-hematologic toxicity that represents at least 2 grade increase from baseline, is attributed to veliparib treatment and requires a treatment delay of > 14 days in initiation of Cycle 2
4. Any toxicity that represents at least 2 grade increase from baseline, is attributed to veliparib treatment and requires at least one of:

- a. Dose modification within Cycle 1
- b. Omission of carboplatin, > 1 daily etoposide dose, or > 30% veliparib doses in Cycle 1

Subjects experiencing DLT(s) during the DLT observation period will require an interruption of study drugs and possible discontinuation from further participation in the study. Veliparib may be reintroduced at a reduced dose, if the toxicity returns to  $\leq$  Grade 1 or to baseline if Grade 2 at study entry. All decisions regarding continued dosing for individual subjects experiencing a DLT will be medically managed by the investigator in conjunction with the AbbVie TA MD.

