#### **Veliparib Effect on Etoposide Pharmacokinetics Parameters**

For the dose escalation subjects, a linear mixed effects model analysis will be performed for dose normalized  $C_{\max}$ ,  $AUC_{0-24}$  and  $AUC_{\infty}$ , to compare etoposide pharmacokinetics parameters when co-administered with veliparib (Cycle 1 Day 1) relative to etoposide administered alone (Cycle 2 Day 1). For  $C_{\max}$  and AUC, the logarithmic transformation will be used unless the data indicate that the logarithm has significant non-normality. The model will include effects for visit (Cycle 1 Day 1, Cycle 2 Day 1). The within-subject variability will be accounted for utilizing the repeated statement for the effect of visit. Within the repeated measure analysis modeling framework, the null hypothesis of no difference between etoposide in combination with veliparib and etoposide alone will be tested with a significance level of 0.05. The relative bioavailability of etoposide co-administered with veliparib relative to etoposide alone will be estimated. Point estimates and corresponding 90% confidence intervals for the ratio of etoposide co-administered relative to etoposide alone will be provided. The point estimates will be obtained by antilogarithm of the estimate of the difference of the logarithmic means. The 90% confidence intervals will be similarly obtained by antilogarithm of the endpoints of the corresponding confidence intervals for the difference of mean logarithms obtained within the framework of the repeated measure analysis model.

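### Veliparib dose proportionality rests on two tests of no difference in small Phase 1 cohorts, with no ratio, slope or confidence interval planned, so a non-significant result could not support it

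*Protocol*

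**What the plan says.** Protocol 8.1.6.2 opens the topic with "To address the issue of dose proportionality for designated veliparib doses, a linear mixed effects model analysis will be performed". The outcomes are dose-normalized Cmax and AUC from 0 to 8 hours, normally log-transformed. Two inferences follow. First, "the null hypothesis of no difference between the means of the highest and lowest veliparib doses will be tested". Second, provided at least four dose levels are studied, "a test will also be performed on a contrast in the dose level", chosen to be sensitive to a roughly linear trend in dose or log dose. The only significance level in this subsection concerns keeping covariates, which requires that "the regression coefficient be significant at level 0.10". No level is given for the two proportionality tests. Nor is there an effect estimate, an interval or guidance on reading a non-significant result.

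The next subsection, on etoposide, pairs its test (at 0.05) with estimation: "Point estimates and corresponding 90% confidence intervals for the ratio of etoposide co-administered relative to etoposide alone will be provided".

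On numbers, Protocol 5.1 says "A minimum of 3 evaluable subjects will be enrolled at each dose level". Table 4 allows 3 to 9 subjects at level I and 3 to 6 at each other level. The text after Table 5 adds that "a total of at least 9 subjects will be treated at the RPTD". The overall figure is also in 5.1: "The study was designed to enroll approximately 35 subjects in Phase 1". The SAP (4.2) covers Phase 2 only and leaves Phase 1 and pharmacokinetic analyses to other reports.

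**The concern.** If exposure is proportional to dose, dose-normalized exposure is the same at every level. That is a claim of similarity, and here similarity is the null hypothesis of both tests. A large P value may mean that the doses behave alike, or that there were too few subjects to tell. With a handful of subjects per level compared between subjects, the second explanation is hard to dismiss. A small P value does not say whether the departure is large enough to matter.

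At stake is the quality of one pharmacokinetic statement: the planned inference would not show how far from proportional exposure could be over the doses studied.

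**Working it through.** The documents give no power, alpha or variability for this analysis, so there is no planned figure to reproduce. The check asks how often the two tests would miss a stated departure.

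**Inputs from the protocol.** Five levels, 80, 120, 160, 200 and 240 mg (5.1, Table 4); cohort sizes as above; about 35 subjects in total.

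**Assumptions.**
- Two-sided alpha 0.05, with 0.10 as a sensitivity.
- CV of dose-normalized exposure 15% to 50%, read as what remains after any covariates.
- True 240-to-80 mg ratio of dose-normalized exposure R = 1.25, with 1.5 for comparison.
- Four layouts from 80 to 240 mg: 3/3/3/3/9 (N = 21), 6/6/6/6/11 (35), 3/3/6/9/14 (35), 9/6/6/6/9 (36). The 11 and 14 at 240 mg, and the 9 at 200 mg, are assumed sizes, not protocol figures.

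**Formulas.** Log-scale SD: s = sqrt(ln(1 + CV²)).
- Highest versus lowest: SE = s × sqrt(1/n_low + 1/n_high), df = N − 5, noncentrality ln(R)/SE.
- Trend: slope of ln(dose-normalized exposure) on ln(dose), SE = s/sqrt(Sxx), where Sxx is the sum of squares of ln(dose) about its mean; df = N − 2, true slope ln(R)/ln(3).
- Miss rate = 1 − power from the noncentral t distribution.

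**One layout in full: 6/6/6/6/11, CV 40%, R = 1.25.**
- s = sqrt(ln 1.16) = 0.385.
- Highest versus lowest: SE = 0.385 × sqrt(1/6 + 1/11) = 0.196. Noncentrality = 0.223/0.196 = 1.14 on 30 df. Miss rate 80%.
- Trend: Sxx = 5.49, SE = 0.385/sqrt(5.49) = 0.164, true slope = 0.223/1.099 = 0.203. Noncentrality 1.23 on 33 df. Miss rate 78%.
- Largest observed ratio still non-significant in the pairwise test: exp(2.042 × 0.196) = about 1.49.

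**Range over the four layouts, R = 1.25, two-sided 0.05.**

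| CV | Highest vs lowest, missed | Trend, missed |
|---|---|---|
| 15% | 13-44% | 8-36% |
| 20% | 36-64% | 29-58% |
| 30-50% | 65-90% | 60-89% |

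**Sensitivities.**
- Two-sided 0.10, CV 30%: 53-71% (highest vs lowest) and 47-67% (trend).
- R = 1.5, two-sided 0.05, CV 30-50%: 19-77% and 13-73%. In the 6/6/6/6/11 layout at CV 40%: 48% and 41%.

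**What an interval would show.** 90% confidence interval for the highest-to-lowest ratio when the observed ratio is exactly 1.00 (29 df):

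| Subjects | CV 20% | CV 30% | CV 40% |
|---|---|---|---|
| 6 vs 9 | 0.84-1.19 | 0.77-1.30 | 0.71-1.41 |
| 3 vs 9 | 0.80-1.25 | 0.72-1.39 | 0.65-1.55 |

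With a CV of about 30% or more, even a perfect observed match would not rule out a 1.25-fold departure. The interval makes this visible; a P value of 1.0 would not.

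**The case against.** Several points on the other side are sound.

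- **No decision rule is stated.** A reader might infer that P above alpha will be reported as proportional. The protocol never says so. It says only that hypotheses will be tested.
- **A flat miss rate of 60-90% is not supported.** It needs an assumed CV of 30-50% and two-sided 0.05. No document sets a 30% floor, and the planned covariates (age, weight, gender and others) could lower the residual variability. At CV 15-20% the rates run from 8% to 64%.
- **Large departures are not generally missed.** A reader might extend the concern to 50%. In the layout worked above, a 1.5-fold difference is missed 48% and 41% of the time, so detection is somewhat more likely than not.
- **The tests are not the only output.** Protocol 8.1.6.1 tabulates parameters with summary statistics by dose level. The model may also take dose as continuous, although nothing commits to reporting the slope.
- **The etoposide analysis is not a full parallel.** It is within-subject and serves a primary Phase 1 objective (Protocol 4.0). Proportionality is not a listed objective.
- **The consequence is small.** Protocol 3.3.2 already describes exposure as roughly dose proportional from 10 to 500 mg BID, on preliminary data from six studies. The Phase 2 dose was chosen on toxicity and is already fixed.

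These points limit the magnitude and importance. They do not remove the defect. By-dose summaries give neither a between-dose ratio nor its uncertainty, and at any CV a test of no difference cannot support similarity. The different design of the etoposide analysis is no reason to omit an interval here.

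**Conclusion.** The concern holds as a minor point of method. The inference planned for dose proportionality consists of two tests whose null is the property in question, with no estimate, interval or alpha. A non-significant result would be uninformative about proportionality unless variability were low.

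The size is conditional. For a 1.25-fold departure over 80 to 240 mg, at two-sided 0.05 and in layouts of 21 to 36 subjects, it is missed about 8-44% of the time at CV 15%, 29-64% at CV 20%, and 60-90% at CV 30-50%. CV, alpha, the 1.25-fold figure and the exact layouts are all assumptions. The conclusion about method depends on none of them. No Phase 2 endpoint or analysis is affected.

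**What to change.** In Protocol 8.1.6.2, or in the separate Phase 1 pharmacokinetic analysis plan:

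1. Report the highest-to-lowest ratio of dose-normalized geometric means, and/or the slope of ln(exposure) on ln(dose), each with a 90% confidence interval, for Cmax and AUC.
2. Base any statement on proportionality on that estimate and interval.
3. Keep the two P values as supportive, at a stated alpha and sidedness.
4. State that non-significance is not evidence of proportionality.

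A fixed acceptance range is optional. If one is wanted, a ratio of 0.80 to 1.25 over this 3-fold dose range corresponds to a slope of about 0.80 to 1.20, since 1 ± ln(1.25)/ln(3) = 1 ± 0.203. That range is a choice to be justified, not a requirement of the documents.

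The cost is a few sentences and a few lines of code, with no new samples or subjects. The drawback is that with these cohort sizes the interval will probably be wide and the result may be inconclusive.
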